Inclusion/Exclusion Criteria: [List ALL inclusion and exclusion criteria. Any proposed exclusion criterion based on gender (women of childbearing potential), age, or race must include justification for the exclusion. Describe the conditions under which participants may be removed from the study, i.e., noncompliance with study rules, study termination, etc.]

Smartphone users ages 18-65 with a BMI 27-45 will be recruited for this study. Participants must log into a social media platform on a daily basis and engage (like, reply, post) at least 4 days per week.

Age justification: Weight loss interventions intended for ages outside of the range (<18 or >65) require individualized attention from a physician and will not be appropriate to use the DPP.

Participants will be excluded if they:

- 1. Do not have a smartphone;
- 2. Are unable to get medical clearance from their PCP;
- 3. Have plans to move during study;
- 4. Are not interested in losing weight;
- 5. Have Type 1 Diabetes or uncontrolled Type 2 Diabetes (as determined by PCP);
- 6. Have medical conditions that would prevent increasing physical activity or making dietary changes;
- 7. Are pregnant/lactating or plans to become pregnant during study;
- 8. Are currently taking medication affecting weight;
- 9. Currently participating in a clinical weight loss program to assist them with weight loss (e.g. Weight Watchers, Sparkpeople, etc);
- 10. Unable to walk at least ¹/₄ mile unaided without stopping;
- 11. Experienced a weight loss of 5% or more in past 3 month;
- 12. A history of/or plans on having bariatric surgery;
- 13. Did not complete the baseline measures;
- 14. Not willing to use Twitter, or if a current Twitter user, not willing to create an new account specifically for study purposes;
- 15. Participated in another weight loss study under the direction of the PI of this study;
- 16. Current smoker (smokes 3 or more cigarettes per day);
- 17. Unavailable to attend weekly group meetings;
- 18. Prefers one condition over another;
- 19. Score of 30 or higher on the BDI or endorsement of 2 or 3 on BDI #9 indicating suicidal thoughts;
- 20. Presence of binge eating disorder;
- 21. Did not complete the orientation webinar;
- 22. Are unable to provide consent due to mental illness or a cognitive impairment;
- 23. Does not speak English; or
- 24. Are a prisoner

Participants will be withdrawn from the study if: they drop from participation, do not complete all baseline procedures, disrupt in-person groups, or post inappropriate content on Twitter. Participants reporting that they would like to withdraw from the study will be given the option to: 1) withdraw from all intervention-related activity and contacts, but still complete the final assessment or 2) withdraw from the study completely with no additional study contact. If a participant becomes pregnant during the study, they will be withdrawn from the intervention, but will be given the option still complete the follow-up assessments.

Potential Harms/Risks and Inconveniences: [Describe the potential risks to participants (and secondary participants, if applicable) and **steps taken to minimize risks** for each participant population. Assess the likelihood of the risk occurring and, if it were to occur, the seriousness to the participant. Types of risks to consider include, but are not limited to: physical, psychological, social, legal, employment, and financial. Also describe any anticipated inconveniences the participants may experience (time, abstention from food, etc.).]

Possible risks for being in this study includes: Injury while exercising, breach of confidential information, and discomfort completing measures. The attempt to avoid risks to participants will be addressed by: suggesting moderate intensity exercise to avoid discomfort, pain, or injury. Participants reporting discomfort will be referred to their PCP. Injuries are unlikely to occur since we screen out medical conditions that could make someone prone to injury, we obtain medical clearance, and we only suggest moderate activity. We also provide participants with information on exertion level and remind them to see medical attention if there is pain. Tracking data will be stored electronically in REDcap, a network secure data entry program; any data on paper will be stored in a locked file cabinet; and participants will be informed that they may withdraw from the study at any time if they feel discomfort with any of the study procedures.

For Get Social participants only: To maintain confidentiality, participants will be asked not to use their real name, locations, or contact information for their user information or in there tweets; they will be asked to only use user names when talking to other study participants; they will also be asked not to disclose that they are in a research study to protect confidentiality of other participants; tweets from the participants will be continuously

collected and monitored using computer programming and will address any issues related to privacy. We will do this by assigning a staff member to read and assess each interaction in the group on a daily basis. Any privacy-related problems will be brought to the attention of the PI and Co-I's immediately.

Benefits: [Describe anticipated benefits to the individual participants. If test results will be provided, describe and explain procedures to help participants understand the results. If individual participants may not benefit directly, state so here. Describe anticipated benefits to society (i.e., added knowledge to the field of study) or a specific class of individuals (i.e., athletes or autistic children). Do not include compensation or earned course credits in this section.]

Participants may or may not benefit from participating in the study. Benefits that could occur are losing weight through the exercise and lifestyle intervention. Societal benefits include providing evidence to support an intervention delivery modality that is more conducive to settings like worksites, health plans, and clinics that serve large populations but have limited space, staffing, and resources for traditional in person interventions.

Risk/Benefit Analysis: [Describe the ratio of risks to benefits. Risks to research participants should be justified by the anticipated benefits to the participants or society. Provide your assessment of anticipated risks to participants and steps taken to minimize these risks, balanced against anticipated benefits to the individual or to society.]

The possible risks of the study (including injury during exercise, psychological discomfort, and breach of confidentiality) are minimal and are outweighed by the possible benefits to participants (weight loss).

Economic Considerations: [Describe any costs to the participants or amount and method of compensation that will be given to them. Describe how you arrived at the amount and the plan for compensation; if it will be prorated, please provide the breakdown. Experimental or extra course credit should be considered an economic consideration and included in this section. Indicate when participants will receive compensation.]

Economic burden to subjects includes the time needed for screening and study participation. My Fitness Pal is freely accessible. Additionally, there is no cost to participants for attending study visits. Depending on smartphone data usage plan for each participant, usage charges may incur due to increased use of mobile apps such as Twitter and My Fitness Pal.

Participants will be paid in the form of online Amazon gift cards. Participants will receive \$30 for completing the baseline procedures. If participants complete the 6 month assessment within the 2-week target window, we'll provide \$40 compensation; otherwise we'll provide \$30. If participants complete the 12 month assessment within the 2-week target window, we'll provide \$60 compensation; otherwise we'll provide \$45. Payment will be in the form of an online gift card paid after each assessment. The procedures for each assessment will need to be completed before providing compensation, including all 3 24hr recalls.

At each time point, gift cards will be purchased and sent to participants within two weeks of the final participant in each group completing the associated procedures to decrease administrative time.

Data Safety Monitoring: [This is a prospective plan set up by the study investigators to assure that adverse events occurring during studies are identified, evaluated, and communicated to the IRB in a timely manner. Although the investigators initially propose a Data Safety Monitoring Plan (DSMP), the IRB must approve the plan and may require revision of the plan. A DSMP is required for all human studies at the University of Connecticut except for studies determined to be exempt from continuing IRB review. For studies that present more than minimal risk to participants, the IRB will review and determine on a case-by-case basis whether a data safety monitoring board is most appropriate. Please refer to the IRB's policy regarding data safety monitoring before completing this section - http://research.uconn.edu/policies-procedures.

Issues that should be addressed in the DSMP include the following:

- 1. frequency of the monitoring
- 2. who will conduct the monitoring (Under UConn policy a student cannot be the sole person responsible for monitoring the data and safety of the protocol procedures.)
- 3. what data will be monitored (include compliance with approved IRB protocol.
- 4. how the data will be evaluated for problems
- 5. what actions will be taken upon the occurrence of specific events or end points
- 6. who will communicate to the IRB and how communication will occur
- 7. describe procedures to inform the sponsor

Sample response to issues listed above for minimal risk/slight increase over minimal risk – "Survey results will be monitored by the PI in conjunction with the student investigator once every two weeks (items 1, 2 and 3). Survey responses will be reviewed to monitor for clarity (i.e., the same question is skipped by 5 or more participants). In that case, the question will be revised and an amendment will be submitted to the IRB (items 4, 5 and 6)."

A DSMB has been set up for this study and convene twice a year. DSMB reports are produced by the program director and data manager. Reports will be reviewed by the principal investigator and the study statistician then will be sent safety officers on the board. Recruitment reports are generated and emailed at the end of each recruitment wave and a full data report is generated and reviewed during a meeting twice a year:

Report type	Frequency of review
Recruitment rates	Twice per year and at the end of each recruitment wave
Inclusion/exclusion	Twice per year and at the end of each recruitment wave
Demographics	Twice per year and at the end of each recruitment wave
Adherence to study protocols	Twice per year
Adverse events	Twice per year
Participant Retention/Engagement	Twice per year
Data review (completeness/outliers)	Twice per year

Qualifications and responsibilities of the Safety Officer

The safety officers for this project are [name], Assistant Professor at Rosalind Franklin University, North Chicago, IL and [name], Professor at University of Massachusetts Amherst. [name] has a degree in clinical psychology, experience in exercise and weight loss interventions, and an understanding of the types and severity of injuries commonly experienced during weight loss trials. [name] has expertise in inference, mixed models, sampling, longitudinal data analysis, and cluster randomized trials.

Recruitment rates and adherence inclusion/exclusion criteria, and ethnic diversity goals:

Recruitment progress will be reviewed at the end of each recruitment phase, which will occur 3-4 times per year. Inclusion/exclusion criteria and diversity goals will be reviewed twice per year. This review will ensure that project deadlines are being met, that participants meet eligibility criteria, and that the ethnic diversity goals outlined in the grant proposal are being met.

Adherence to study protocols:

The principal investigator will: direct creation of all study protocols and will be involved in trainings and supervision of all study staff. Quality control will be conducted in all phases of the project. All visits will be audio recorded. A 10% randomly selected sample of the recordings will be assigned to the co-investigator and project director for review. A summary will be provided to the safety officers and a checklist will be completed for each review.

Adverse events:

Baseline participants who report conditions that could create a safety concern while receiving the intervention will be excluded. Adverse events that occur during the intervention will be assessed, recorded, and followed up until resolved. Safety monitoring procedures will be documented in a standard protocol and overseen by the PI and program director. Any adverse events will be immediately reviewed by the program director. The safety officers will be informed during monthly reports for all adverse events. Serious adverse events will be communicated

immediately to the safety officers. The NIH, UConn, and UMMS IRB will be notified immediately in the event of serious adverse event. Any death of a study participant will be reported to the NIH, UConn and UMMS IRB whether or not it appears to be related to the study.

The adverse event report will include a listing of adverse events including duration, severity, seriousness, relatedness, action taken, and resolution. This information will be presented unblinded. A significant increase in the rate of adverse events in one treatment group would be cause for concern for the safety of participants in the study. p to the safety officer.

Participant retention

Attendance will be collected at all study visits. If a participant misses a group, materials will be sent to them and a make-up session will be offered. If a participant chooses to drop from the intervention, they will be given the option to skip the rest of the intervention visits, but still complete the final assessment. Compliance information (number/percent of intervention visits attended; engagement in Twitter private group) will be provided in a report to the safety officers.

Data Security:

The databases will be maintained on UConn and UMass servers where security will be maintained through access controls. The program director will control the database and surveys and will allow access to necessary staff. Staff wanting access to identifiable data will need to: have prior IRB approval to be on the project, apply for a REDCap account, be approved by the program directo, and utilize a password for login.

Data review (completeness/outliers):

Data reports will be reviewed by the data manager, project director, statistician, and PI. Reports will include completeness of data (visits completed, online engagement, % of expected forms submitted, % of submitted forms passing edit); missed visits and missing information within visits; descriptive information for each endpoint (change in weight and physical activity) without statistical testing; and quality control analyses for primary outcome (change in weight).

Privacy/Confidentiality Part 1: [Explain how the privacy interests of participants will be maintained during the study (note that **privacy pertains to the individual not to the data**). Describe how data will be coded. Do not use the any potentially identifiable information such as initials of participants as part of the code. If identifiable, sensitive information (illegal drug use, criminal activity, etc.) will be collected, state whether a Certificate of Confidentiality will be obtained. Be sure to state whether any limits to confidentiality exist and identify any external agencies (study sponsor, FDA, etc.) that will have access to the data. If participants will be screened, describe the plans for storage or destruction of identifiable data for those that failed the screening.]

REDCap will be used for data entry and management. Digital recorders will be used for recording audio from the groups. The database and recordings will be maintained on UMass and UConn servers where security will be maintained through access controls. Once recordings are saved on the server they are deleted from the recorder. Recordings are used only for quality control and will not be transcribed. Access to the files require permission from the program director, a UMass/UConn password, and IRB personnel approval. For each user, REDCap will require a REDCap profile, username and password to enter the program. Staff will only have access to the database if the data manager has given them access. UMass and UConn IRBs and their representatives, and study personnel will have access to the research data, as will the study sponsor if requested. All participants will be assigned an ID number, which will link them to their study data. PHI fields will be stored in a separate form from other data collection forms. Data will be completely de-identified once the last assessment phase is complete. At this time the link between ID number and study data will be destroyed. Study data in the form of hard copies will be stored in a locked file cabinet managed by the program director and will be destroyed 3 years after completion of the study.

Data from ineligible participants:

Contact information will be stored in a file with an indication that they are not eligible. However the data collected from the screening, including reason ineligible, will be stored in a separate de-identified file.

Privacy/Confidentiality Part 2: Complete the Data Security Assessment Form: [This form IS REQUIRED for ALL studies. The form is available here - http://research.uconn.edu/irb/irb-forms-infoed/. This form will be used to assess procedures for protecting confidentiality of data collected during the study and stored after closure. It will also be used to assess plans for storage and security of electronic data in accordance with University Best Practices. Review the document proving tips to complete the form located at http://content.research.uconn.edu/pdf/storrs/rcs/irb/TipsDataSecurityAssessmentForm.docx.

This form has been completed.

Informed Consent

As PI, you are responsible for taking reasonable steps to assure that the participants in this study are fully informed about and understand the study. Even if you are not targeting participants from "Special Populations" as listed on page 4, such populations may be included in recruitment efforts. Please keep this in mind as you design the Consent Process and provide the information requested in this section.

Consent Setting: [Describe the consent process including who will obtain consent, where and when will it be obtained, and how much time participants will have to make a decision. Describe how the privacy of the participants will be maintained throughout the consent process. State whether an assessment of consent materials will be conducted to assure that participants understand the information (may be warranted in studies with complicated study procedures, those that require extensive time commitments or those that expose participants to greater than minimal risk).]

The consent process will take place at the beginning of the baseline appointment. Ample time will be allowed for discussion or questions. Consent will be obtained by research assistants/coordinators trained in the consent process. To ensure that participants are given enough time as needed to review the consent form, they will be emailed the consent form prior to the baseline appointment.

The interventionists will receive an online survey at the 6-month time point of each wave. An information sheet appears on the first page in place of a signed consent form. They will as much time as needed to review the information sheet and email/call staff for questions. They may also decide not to complete the survey.

Capacity to Consent: [Describe how the capacity to consent will be assessed for participants with limited decisionmaking capacity, language barriers or hearing difficulty. If a participant is incapable of providing consent, you will need to obtain consent from the participant's legal guardian (please see the IRB website for additional information).]

To be able to actively participate in the study, participants must be adults without impaired decision making ability that are able to speak and read English. The consent process will include a discussion of the participants understanding of what participating in research means including their rights as a research participant, the protocol, as well as risks and potential benefits to participating in the study. If research personnel obtaining consent believes there is a concern regarding a participant understanding participation will be discussed with the program director who will determine whether to exclude the participants on this basis.

Parent/Guardian Permission and Assent: [If enrolling children, state how many parents/guardians will provide permission, whether the child's assent will be obtained and if assent will be written or oral. Provide a copy of the script to be used if oral assent will be obtained.]

N/A

Documentation of Consent: [Specify the forms that will be used for each participant population, i.e., adult consent form, surrogate consent form, child assent form (written form or oral script) or an information sheet. Copies of all forms should

be attached to this application in the same format that they will be given to participants (templates and instructions are available on the IRB website).]

Adult consent form will be used for the study participants and an information sheet for the interventionists.

Waiver or Alteration of Consent: [The IRB may waive or alter the elements of consent in some minimal risks studies. If you plan to request either a *waiver of consent* (i.e., participants will not be asked to give consent), an *alteration of consent* (e.g., deception) or a *waiver of signed consent* (i.e., participants will give consent after reading an information sheet), please answer the following questions using specific information from the study:]

Waiver (i.e. participants will not be asked to give consent) or alteration of consent (e.g. use of deception in research):

- *Why is the study considered to be minimal risk?*
- How will the waiver affect the participants' rights and welfare? The IRB must find that participants' rights are not adversely affected. For example, participants may choose not to answer any questions they do not want to answer and they may stop their participation in the research at any time.
- Why would the research be impracticable without the waiver? For studies that involve deception, explain how the research could not be done if participants know the full purpose of the study.
- How will important information be returned to the participants, if appropriate? For studies that involve deception, indicate that participants will be debriefed and that the researchers will be available in case participants have questions.

Waiver of signed consent (i.e. participants give consent only after reading an information sheet):

We are requesting a waiver of signed consent to administer a feedback survey to interventionists and to perform the telephone screening with participant. The screening involves minimal risk and will save staff and participant time in the event of ineligibility by allowing staff to assess criteria before an in-person visit.

• Why is the study considered to be minimal risk?

The survey is minimal risk because it lasts about 10 minutes and includes feedback related to the intervention delivery. We don't ask any sensitive questions. The telephone screening is minimal risk because it lasts about 15 minutes and includes a description of the study and initial eligibility-related questions.

• Does a breach of confidentiality constitute the principal risk to participants? Relate this to the risks associated with a breach of confidentiality and indicate how risks will be minimized because of the waiver of signed consent.

The ability to complete the short survey online at their own comfort reduces the possibility of any discomfort of unnecessary travel to our location to provide in-person consent. During the telephone screening, we ask for permission to ask questions and indicate that they may choose not to answer.

• Would the signed consent form be the only record linking the participant to the research? Relate this to the procedures to protect privacy/confidentiality.

No. We also have financial forms that are utilized to pay them for delivering the intervention and their first and last names are known to all study subjects. Performing a telephone screening will save staff and participant time in the event of ineligibility by allowing staff to assess criteria before an in-person visit.

• Does the research include any activities that would require signed consent in a non-research setting? For example, in non-research settings, normally there is no requirement for written consent for completion of questionnaires.

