We powered the study to be able to detect non-inferiority for the primary outcome, percent weight loss at 12 months. Thus detectable effect sizes for secondary outcomes (Aim 1), cost (Aim 2), and predictors of weight loss in the Get Social condition (Aim 3) are based on the N available to evaluate non-inferiority of the primary outcome. Interventionist sample size was determined based on the availability of the interventionist and a balance of conditions being led by each coach.

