Aim 1: Efficacy. Our sample size estimates utilize methods developed specifically for non-inferiority trials.72 In a non-inferiority trial, the null hypothesis (H0) is that the new treatment is inferior to the standard treatment, and the alternative hypothesis (HA) is that the new treatment is not inferior to the standard treatment. "Not inferior to" is defined by the non-inferiority margin, δ . Here, we set $\delta = 2\%$, based on a clinically meaningful difference in average weight loss between the two treatment arms. This means that if the Get Social condition loses up to 2% less weight on average than the Traditional condition, we will consider the Get Social condition to be non-inferior to the Traditional condition. If the Get Social condition loses >2% less weight then it will be considered inferior to the Traditional condition. Thus, adequate power for clinical non-inferiority requires a sample size such that there is better than 90% probability that the lower limit of the confidence interval lies above $-\delta$, if the true effect size is zero or above. We estimated SD=5.5% based on our previous, fully powered randomized trial.28 With alpha=0.05, and δ =2%, we have 90% power to conclude that the Get Social condition is not inferior to the Traditional condition with 131 participants per arm. Accounting for 20% attrition, we will enroll 328 participants total (164 per arm). We considered adjusting the sample for intraclass correlation but previous research shows that weight loss does not cluster among members of weight loss treatment groups.1 We do not believe that the social influence in online groups will be stronger in the Get Social condition. Studies of social influence suggest that team-based activities or recruiting relatives or friends can lead to weight loss clustering but we will not be using such an approach.1 That said, we do believe that after the intervention, peer-to-peer engagement may continue for longer because participants will continue to have a channel by which to communicate with one another. They will also have the opportunity to collect additional social ties outside of the intervention which may be the source of social support, but this is likely to vary greatly across participants (not within treatment groups) and we do not have evidence that such ties will exert social influence of the magnitude of team-based activities and closer ties (i.e., relatives, friends). Secondary outcomes. For the secondary outcomes, we calculated the non-inferiority margins so that we have 90% power to detect given N=131 per arm, setting α=0.05, and using observed SDs from the literature. For change in kcal/day energy intake at 12 and 18 months, we have 90% to detect that Get Social is not inferior to the Traditional condition with a non-inferiority margin of 182 kcal/day with SD=500 kcal/day.28,56 For change in moderate-to-vigorous intensity physical activity minutes per day at 6 and 12 months, the non-inferiority margin is 9.2 minutes/day with SD=25 minutes/day. For percent weight loss at 12 months, the non-inferiority margin is 2.2% with SD=5.5%.28 If weight losses are more variable at 12 mos than 6 mos, the detectable non-inferiority margin is 3.0% with SD=8.0%.57 Power calculations were conducted using PROC POWER in SAS.73,74

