estimated confidence interval. This analytic approach aims to test whether the Get Social condition is not appreciably worse than (i.e., not inferior to) the traditional condition by our a priori inferiority margin of 2%. The effect estimates will reveal clinical non-inferiority of the Get Social condition if the confidence interval lies completely above $-\Delta$ or clinical non-inferiority of the traditional condition if the confidence interval lies completely below $+\Delta$, i.e., 2%.

Secondary non-inferiority outcomes

Secondary non-inferiority outcomes (dietary intake and physical activity at 12 months) will be examined using the same approach as described for the primary outcome. Linear multivariable models will be used to estimate change in daily caloric intake at 12 months; such models are reasonable given the target sample size and that changes in these outcomes are approximately normally distributed. We anticipate using log transformation to estimate change in physical activity variables, given that physical activity data tends to be skewed. The distribution of secondary outcomes will be explored graphically and inform the primary outcome analysis; analyses will be modified as needed through transformation of the data.

Cost

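### The secondary non-inferiority margins are detectable differences with no stated clinical basis, and 12-month percent weight loss carries two conflicting margins (2% and 2.2%)

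*Protocol*

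**What the plan says.** In the protocol's Justification of Sample Size, the opening text says that effect sizes for the secondary outcomes "are based on the N available to evaluate non-inferiority of the primary outcome". Under Aim 1, the primary margin of 2% is presented as a clinically meaningful difference, and with that margin and SD 5.5% "we have 90% power to conclude that the Get Social condition is not inferior to the Traditional condition with 131 participants per arm".

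The secondary margins are set differently: "we calculated the non-inferiority margins so that we have 90% power to detect given N=131 per arm". The same sentence fixes α at 0.05 and takes the SDs from published work. Four values follow:

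- energy intake: 182 kcal/day at SD 500;
- moderate-to-vigorous activity: 9.2 minutes/day at SD 25;
- "For percent weight loss at 12 months, the non-inferiority margin is 2.2% with SD=5.5" percent;
- "If weight losses are more variable at 12 mos than 6 mos, the detectable non-inferiority margin is 3.0% with SD=8.0" percent.

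The Data Analysis section of the protocol says that diet and activity at 12 months "will be examined using the same approach as described for the primary outcome". It does not restate their margins, and it expects activity to be log-transformed.

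The SAP applies the 2% margin to 12-month percent weight loss. It keeps a section headed as secondary non-inferiority outcomes, but that section contains no margin. Caloric intake is modelled as a change at 12 months. Activity becomes the proportion reaching 150 or more minutes/week, analysed by generalized estimating equations with a logit link.

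**The concern.** A non-inferiority margin should be the largest loss one is prepared to accept. A margin solved from sample size, power and SD answers another question: what the trial can rule out. Such a number widens whenever the outcome is noisier, as the move from 2.2% to 3.0% shows when the assumed SD rises from 5.5% to 8.0%. A claim of non-inferiority for diet or activity against such a number would rest on the enrolment target, with no written judgement about acceptable loss behind it.

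The two margins for one endpoint raise a separate problem. A lower confidence limit of −2.1% for 12-month percent weight loss would fail the 2% margin and pass the 2.2% margin. The protocol should not leave both in place.

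**Working it through.** **Inputs** (protocol, Justification of Sample Size, Aim 1): 131 evaluable per arm, 1:1 allocation, 90% power, α = 0.05, true difference 0, and SDs of 5.5%, 500 kcal/day, 25 minutes/day and 8.0%. Sidedness is not stated. The rule is only that "there is better than 90% probability that the lower limit of the confidence interval lies above" the negative margin, with no confidence level. I therefore tried one-sided 0.05 (90% interval) and one-sided 0.025 (95% interval).

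**Step 1: reproduce the primary sample size.** n per arm = 2·SD²·(z₁₋α + z₀.₉₀)² / δ².

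- One-sided 0.05: 2 × 5.5² × (1.645 + 1.282)² / 2² gives 130 by the normal approximation and 131 by the noncentral t. Then 131 / 0.80 = 163.75, so 164 per arm and 328 in total. This matches the protocol.
- One-sided 0.025: 159 (normal) or 160 (t). This does not match.

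The primary calculation therefore used one-sided 0.05.

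**Step 2: margin detectable with 131 per arm at 90% power.** Margin = SD × √(2/131) × (z₁₋α + z₀.₉₀), with √(2/131) = 0.1236. The margin/SD ratio must then be the same for every outcome: about 0.362 at one-sided 0.05 and 0.401 at one-sided 0.025. The table gives noncentral-t values (260 df).

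| Outcome | Stated margin | Margin/SD | Exact margin, 0.05 | Power at stated margin, 0.05 | Exact margin, 0.025 | Power at stated margin, 0.025 |
|---|---|---|---|---|---|---|
| Weight, primary (SD 5.5%) | 2% | 0.364 | 1.99% | 90.2% | 2.21% | 83.5% |
| Energy intake (SD 500) | 182 kcal/day | 0.364 | 181.3 | 90.2% | 201.0 | 83.5% |
| Activity (SD 25) | 9.2 min/day | 0.368 | 9.06 | 90.8% | 10.05 | 84.3% |
| Weight, secondary (SD 5.5%) | 2.2% | 0.400 | 1.99% | 94.3% | 2.21% | 89.7% |
| Weight (SD 8.0%) | 3.0% | 0.375 | 2.90% | 91.7% | 3.22% | 85.6% |

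No single convention fits every row. Only the 2.2% row clearly departs from one-sided 0.05. It fits one-sided 0.025, or else would need an SD of about 6.08% (2.2 / 0.3616) in place of 5.5%.

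**Step 3: follow the margins into the analysis.** The 2% margin is the only one that either analysis section states. The 182 kcal/day figure is the only margin for caloric intake in either document, and the SAP does not carry it forward. The 9.2 minutes/day figure is on a raw-minutes scale. It does not apply directly to the log scale anticipated in the protocol, and it cannot apply to the binary outcome in the SAP.

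**The case against.** The best defence is that much of this has been overtaken. The SAP applies only the 2% margin to weight, drops the sentence that sends the secondary outcomes through the primary approach, and changes activity to a scale where 9.2 minutes/day has no role. The protocol itself introduces the secondary figures as detectable effect sizes. All of that stands, and it limits the practical weight of the point. It does not settle it: the SAP still groups these outcomes under a non-inferiority heading without giving a margin, so any such claim would rest on a back-solved number or on none.

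Three stronger readings are tempting, and the documents do not support them.

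- **Most of the figures fail to reproduce.** At one-sided 0.05, 182 kcal, 9.2 minutes and 3.0% give 90.2%, 90.8% and 91.7% power. The last two are slightly wide but still deliver the stated 90%. Only 2.2% fails.
- **A shortfall of 9.2 minutes/day would be called non-inferior.** That is 64 minutes/week (9.2 × 7), or 37% of the 175-minute weekly goal. But the rule needs the whole interval above the margin. With a standard error of 25 × 0.1236 = 3.09, the largest observed shortfall that passes is about 9.2 − 1.65 × 3.09 = 4.1 minutes/day (29 minutes/week) at one-sided 0.05, or about 3.1 (22 minutes/week) at one-sided 0.025.
- **The margins are clinically meaningless.** The documents show only that no clinical rationale was written down.

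**Conclusion.** The point holds for the secondary outcomes. By the protocol's own account, the four figures were solved from 131 per arm and 90% power. They are detectable differences, and no clinical basis is stated for any of them. One is an error as written: 2% and 2.2% cannot both be the 90%-power margin for the same endpoint, SD, sample size and α. The 2.2% is about 0.2 percentage points too wide at the error rate behind the sample size.

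The primary 2% margin and the 131/328 sample size are sound at one-sided 0.05. That rate is inferred from the arithmetic, since neither document states it. If a 95% interval (one-sided 0.025) were intended, the primary comparison would have about 83–84% power with 131 per arm, and 90% power would need 159–160 evaluable per arm (199–200 enrolled per arm, about 398–400 in total). This is why the level has to be written down.

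The mixed figures may be left over from a plan with a different primary time point: the text compares variability at 12 and 6 months, and places energy intake at 12 and 18 months although follow-up ends at 12. That is an inference, and the conclusion does not depend on it.

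**What to change.** 1. State the one-sided α, or the confidence level, for non-inferiority once, in both the protocol and the SAP.
2. Delete the 2.2% and 3.0% margins. Keep the single 2% margin for 12-month percent weight loss.
3. Relabel the remaining secondary figures as detectable differences and recompute them at the stated rate. With 131 per arm and 90% power these are about 181 kcal/day and 9.06 minutes/day at one-sided 0.05, or 201 kcal/day and 10.05 minutes/day at one-sided 0.025. Note that the activity figure does not transfer to the binary outcome in the SAP.
4. Report caloric intake and activity as between-arm estimates with confidence intervals. Give no non-inferiority verdict unless a clinically argued margin, on the scale actually analysed, is fixed before analysis. Retitle the SAP section to match.

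The cost is wording in two documents, with no new participants or data. The real downside is that two secondary outcomes lose a formal non-inferiority label.
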